### *9.3. Describe other resources available to conduct the research: For example, as appropriate:*

A waiting area with a dedicated front desk staff member will greet the participants when they arrive at the CBRR. For administering the pre-MRI behavioral practice tests, five private testing rooms are available for participant visits at the CBRR. The MRI scanning facility is in close proximity to the CBRR testing facilities in the MRN portion of Domenici Hall. The scanning facility provides MRI-compatible scrubs for each participant.

With respect to equipment, a PC laptop will be available for running pre-MRI behavioral practice tasks at the CBRR. At the MRN, MRI scans will be carried out on a 3T Siemens MRI scanner using a 32-channel head coil. TMS will be conducted at the Psychiatric Neuromodulation Laboratory on the 2nd floor of the Center for Psychiatric Research, in Domenici Hall on the UNM Campus.

## **10. Prior Approvals**

The UNM Main Campus Office of the Institutional Review Board has reviewed the protocol and agreed to defer review of the application to the UNM-HSC

# NONINVASIVELY MODULATING MOTIVATIONAL BRAIN REGIONS

Human Research Protections Office. The current protocol represents the HC arm of a separate protocol that has been approved by the HRPO (#19-053).

## 11. Multi-Site Research

N/A – The current protocol is a single-site study.

## 12. Study Procedures

The study will be conducted in three 3-6 hour sessions which can be arranged to accommodate participants' schedules. The three sessions will take place with no less than 24 hours, and no more than two weeks apart between each study visit. Approximately 24 hours prior to the scheduled date, the participants will receive an email and a phone call including important information for them to be aware of prior to coming in for the study (**Appendix 9**). An IRB-approved member of the research team will greet participants, and will go through the study consent procedures.

SARS-CoV-2 related note: For the duration of the SARS-CoV-2 pandemic, consent procedures will be completed remotely via a HIPAA-compliant Zoom account or phone call, with participants receiving the document via email. They will then sign the consent document when they appear in person for their study visit. A note to file will be created for each consent signed in this way.

Additionally, for the duration of the visit the participant and experimenter will remain physically-distanced as much as possible, will both be wearing face coverings, and the experimenter will also be wearing a laboratory coat to reduce the risk of SARS-CoV-2 spread through droplets. During the TMS protocol, an acrylic divider will be used whenever possible to separate the participant and experimenter. MRI scans will be completed using HRRC approved protocols for scanning during the SARS-CoV-2 pandemic.

**Table 1. Assessments**

Order	Measure	Time (max minutes)
1	Consent + MRI Screen + Demographics	30
2	Rivermead Post Head Injury Questionnaire	10
3	Apathy Evaluation Scale (AES)	5
4	Apathy Motivation Index (AMI)	5
5	Neurobehavioral Symptom Inventory	5
6	NIH-Toolbox Cognition Battery	45
7	Frontal Systems Behavior Scale	10
8	Barratt Impulsivity Scale	5
9	Padua Inventory-Revised	5
10	Meta-Cognitions Questionnaire	5

## NONINVASIVELY MODULATING MOTIVATIONAL BRAIN REGIONS

11	Toronto Alexithymia Scale	5
12	The Next Big Five Inventory	5
13	Beck Anxiety Inventory	5
14	Beck Depression Inventory	5
15	Posttraumatic Stress Disorder checklist	5
16	Substance & Alcohol Use Questionnaires	10
17	Practice of fMRI Task ('Bandit Task')	5
18	Practice of fMRI Task #2 ('Apples Task')	5
ALL	Total	170 minutes

- **Demographics:** The Demographics spreadsheet includes background information on ethnicity, education, alcohol, and medications. It is attached in **Appendix 10**.
- **Rivermead Post Head Injury Questionnaire:** Is a semi-structured, gold standard interview used to assess each participants' TBI history in depth. This is primarily to provide evidence that HC participants in this study have quantifiably fewer / less severe TBI histories than patients in Study #19-053. It is attached in **Appendix 11**.
- **Apathy Evaluation Scale (AES):** Is an 18-item self-report measure used to assess apathy symptoms in individuals with neurological disorders such as TBI. It is attached in **Appendix 12**.
- **Apathy Motivation Index (AMI):** Is an 18-item self-report measure used to assess apathy symptoms in individuals with neurological disorders similar to the AES, but also assays a dimension known as “social-motivational apathy”. It is attached in **Appendix 13**.
- **Neurobehavioral Symptom Inventory (NSI):** The NSI is a 22-item self-report questionnaire designed to probe the specific set of sequelae experienced by patients with TBI. Patients rate the degree to which they have experienced a set of common symptoms on a scale of 0-4, depending on how severely they have disturbed the patient in the past two weeks. It is attached in **Appendix 14**.
- **NIH-Toolbox Cognition Battery (NIH-TB):** The NIH-TB is a comprehensive set of standardized cognitive assessments developed by the NIH to evaluate a range of cognitive functions—including attention, episodic memory, executive function, language, processing speed, and working

## NONINVASIVELY MODULATING MOTIVATIONAL BRAIN REGIONS

memory. These tasks will be administered on an iPad, with a member of the research team supervising the participants' progress and answering any questions they might have. The NIH-TB is not a pen and paper task, and was not programmed by the PI, and is therefore not appended here. However, for reference the NIH has posted a series of demonstration videos on YouTube: <https://www.youtube.com/channel/UC-WnVlfVYm5i5xULhBCjOkQ>

- **Frontal Systems Behavior Scale (FrSBe):** Is a self- or family-report questionnaire comprising 46 items that are highly sensitive to behavioral syndromes that present in patients with frontal brain injury. In particular, the FrSBe provides measures of apathy, disinhibition, and executive dysfunction. We will be using the self-report version in the current protocol.
- **Barratt Impulsivity Scale (BIS):** The BIS is a 30-item self-report questionnaire that is designed to measure several dimensions of impulsivity. Items are rated in terms of frequency (from 1=rarely/never to 4=almost always/always). Principal component analyses of the items on the BIS has suggested that it is comprised of three distinct factors: motor impulsivity (e.g. "I am restless at the theatre or lectures"), non-planning impulsivity (e.g. "I buy things on impulse"), and attentional impulsivity (e.g. "I am self-controlled"). The BIS provides a dimensional measure of each of these factors that is useful for capturing levels of impulsivity in both the subclinical and clinical range. All BIS items are attached in **Appendix 15**.
- **Padua Inventory-Revised (PI-R):** The PI-R is a 39-item self-report instrument that is ideally suited for measuring OC traits in the subclinical and clinical range. Similar to the BOCS, the PI-R breaks down into five factors, including contamination obsessions (e.g. "I feel my hands are dirty when I touch money"), dressing/grooming compulsions (e.g. "I feel obliged to follow a particular order in dressing, undressing, and washing myself"), checking compulsions (e.g. "I have to do things several times before I think they are properly done"), obsession thoughts of harm to self/others (e.g. "I imagine catastrophic consequences as a result of absent-mindedness or minor errors which I make"), and obsessional impulses to harm self/others (e.g. "When I look down from a bridge or a very high window, I feel an impulse to throw myself into space"). Items are rated with respect to intensity, from 1 = "not at all" to 5 = "very much". Scoring details and the items from the PI-R are attached in **Appendix 16**.
- **Meta Cognitions Questionnaire (MCQ):** The MCQ a 30-item self- report instrument that is designed to measure one's beliefs about their degree of access to and control over worry and intrusive thoughts. Anosognosia—i.e. reduced awareness of one's own psychopathology— is often occurs in TBI, it will be critical to evaluate patients' degree of conscious access to their mental states through the MCQ. The MCQ can be broken down into positive beliefs

(e.g. “worrying helps me avoid problems in the future”), negative beliefs (e.g. “my worrying is dangerous for me”), cognitive confidence (e.g. “I have little confidence in my memory for words or names”), need for control (e.g. “I should be in control of my thoughts at all times”), and cognitive self-consciousness (e.g. “I think a lot about my thoughts”). The MCQ-30 is attached in **Appendix 17**.

- **Toronto Alexithymia Scale (TAS):** The TAS is a self-report questionnaire designed to assess one’s ability to identify and describe their own emotions. Participants rate 20 items on a 5-point Likert with respect to agreement (I.e. 1- Strongly Agree to 5- Strongly Disagree). TAS data reliably loads onto three factors: difficulty identifying feelings (e.g. “I am often confused about which emotion I am feeling”), difficulty describing feelings (e.g. “It is difficult for me to find the right words for my feelings”), and externally-oriented thinking (e.g. “I prefer to analyze problems rather than just describe them”). The TAS is attached in **Appendix 18**.
- **The Next Big Five Inventory (BFI-2):** This is a recent revision of the classic big five personality inventory, in which participants rate 60 items related to their personality with respect to their level of agreement (1 = disagree strongly to 5 = agree strongly). The BFI-2, like the original BFI, is designed to classify participants based on their personality in five dimensions: openness, conscientiousness, extraversion, agreeableness, and neuroticism. The BIF-2 is attached in **Appendix 19**.
- **Beck Anxiety Inventory (BAI):** The BAI is a 21-item self-report questionnaire of a variety of somatic (e.g. “hot/cold sweats”) and affective (e.g. “fear of worst happening”) anxious manifestations. Ratings are with respect to frequency of symptoms over the past month, ranging from 0 = “not at all” to 3 = “severely”. The BAI is attached in **Appendix 20**.
- **Beck Depression Inventory (BDI):** The BDI is a 21-item self-report questionnaire of a variety of symptoms of depression, such as boredom (“I am dissatisfied or bored with everything”) and rumination about the future (“I feel the future is hopeless and that things cannot improve”). The BDI is attached in **Appendix 21**.
- **Posttraumatic Stress Disorder Checklist, DSM 5 (PCL-5):** The PCL5 is a 20-item self-report inventory of PTSD symptoms (e.g. “disturbing memories of experience,” “feeling distant or cut off from other people,” etc.), which are rated based on how frequently the participant has experienced those symptoms in the past month. The PCL-5 is attached in **Appendix 22**.

- **Substance Use Questionnaire (SUQ):** The SUQ is a brief self-report inventory dealing with the consumption of alcohol, and both legal and illegal drugs. The SUQ is attached in **Appendix 23**.
- **Alcohol Use Disorder Identification Test (AUDIT):** the AUDIT is a gold standard self-report assay dealing more specifically with the consumption of alcohol and is attached in **Appendix 24**.
- **Bandit Task:** The Bandit task is the gold standard for isolating the neural circuits underlying explore/exploit decision making in humans and nonhuman primates. During this task, participants select between images with varying probabilities of receiving a reward. After learning the reward values of each picture over a series of trials, at random intervals one of the pictures is swapped for a novel picture with a randomly assigned reward value that may be higher or lower than the remaining familiar pictures. This process is repeated for a series of trials, and participants are told that if they score high enough on a randomly selected trial, they will earn a bonus \$20. In actuality, the \$20 will be awarded to all participants as part of the standard compensation rate at the end of the experiment. Therefore, this process will motivate participants to accumulate points on the task, but will be evenly compensated no matter how they do on the task. A random set of pictures will be randomly selected from the International Affective Picture System (IAPS) for each participant. The task was programmed by the PI, and a sample trial image is provided in **Appendix 25**. A brief practice version of the Bandit task will be performed with a research team member prior to the MRI portion on day 1, 2 or 3 of the protocol ( $\approx$ 3 minutes).
- **Apples Task:** The Apples task is an effort-based decision-making task that will be performed during MRI data collection on all days of the protocol. Participants will begin by practicing effortful grips requiring a certain percentage of their maximum voluntary contraction on a dynamometer (%MVC; **Appendix 26**). After experiencing the effort required to execute various %MVC grips, participants will be asked to make a series of reward-effort tradeoff decisions (**Appendix 26**). Each trial will randomly sample the parameter space between 20 and 100%MVC and one to thirteen apples. Participants will be told that at the end of the session the experimenter will select a random set of 10 responses they said ‘yes’ to during the MRI, but in reality (similar to the Bandit task) all subjects will receive a \$20 bonus for completing the task. This will ensure participants are motivated, without placing a burden on them in terms of their physical effort requirement. A brief practice version of the task will be performed with a research team member prior to the MRI portion on day 1 of the protocol ( $\approx$ 5 minutes).
- **TMS Protocol:** On day 2 and 3 of the protocol, single pulses of TMS will be applied over the scalp area overlying the participants’ motor cortex using a

## NONINVASIVELY MODULATING MOTIVATIONAL BRAIN REGIONS

handheld TMS coil (Magventure MagPro; Magventure, Inc., Alpharetta, Georgia, USA). TMS pulses will be delivered through an air-cooled coil in either a figure-eight or double-cone shape, with the latter being particularly useful for targeting deeper structures such as dACC. The first phase of the TMS protocol will involve a standardized motor-thresholding procedure, wherein peripheral responses evoked by single TMS pulses are recorded via an electromyographic recording device (BioPac psychophysiological recording system; BIOPAC Systems, Inc., Goleta, CA). In this phase, the TMS coil's stimulation intensity is titrated to a level that is comfortable yet effective at reliably exciting neuronal populations orthogonal to the coil (50% MEPs  $\geq 50\mu\text{V}$ ; typical duration  $\approx 20\text{-}40$  mins). Then, the repetitive TMS (rTMS) procedure will be administered to a pre-determined cortical target based on the individual's pre-TMS fMRI scan using a Localite Neuronavigation system (TMS Navigator, Localite GmbH, Bonn, Germany; duration  $\approx 10\text{-}20$  mins). The rTMS protocol will involve the delivery of a train of TMS pulses over a cortical target prior to performance of the behavioral tasks during a post-rTMS fMRI scan.

that there is no metal in their clothing, participants will be asked to remove their masks and change into a clean hospital shirt and pants before entering the MRI room. Participants will be given an MRI-compatible surgical face mask provided by MRN to wear during MRI scanning. Participants will perform 4 functional task MRI runs of the Bandit task and the Apples task, which will take approximately 50 minutes total. Additionally, T1-weighted sequence ( $\approx 5$  minutes), a diffusion-weighted scan (dMRI;  $\approx 12$  minutes), and participants will look at a fixation cross for  $\approx 11$  minutes to collect resting state data. Resting state and task MRI runs will be repeated on the second and third sessions post-rTMS delivery, to elucidate the effectiveness of rTMS for engaging the targeted neuronal mechanisms. All task orders will be counterbalanced.

## 13. Data Analysis

### *13.1. Describe the data analysis plan, including any statistical procedures.*

All data will undergo standard preprocessing (e.g. motion correction, spatial normalization) and quality control prior to statistical modeling. Depending on the specific question of the study, data may be analyzed using the general linear model, independent components analysis, machine learning techniques, or a variety of other standard approaches for neuroimaging data.

### *13.2. Provide a power analysis*

Prior studies using fMRI-guided TMS to modulate task-related neural computations have observed effect sizes of approximately  $d \approx 1.02^{67-69}$ , requiring a sample of  $N=17$  per group.

## 14. Provisions to Monitor the Data to Ensure the Safety of Subjects

The protocol is minimal risk. As this study fits NIH criteria for a clinical trial—with subjects prospectively assigned to an intervention—an independent Data Safety and Monitoring Board (DSMB) will review the study data on an annual basis with the PI to ensure participant safety (annual reports to the DSMB—**Appendix 28**). The DSMB for this study will be composed of Drs. [name] (UNM Psychiatry) and [name] (UNM Psychology). Their experience in assuring safety of brain stimulation therapies and seizure monitoring protocols make them ideally suited to serving on this project’s DSMB. Continuous, close monitoring of participant safety will include prompt and frequent reporting of safety data (i.e., adverse/serious adverse events) to the DSMB and the University of New Mexico Health Sciences Center Human Research Protections Office. The PI and members of the DSMB are well-versed in the latest scientific literature on noninvasive brain stimulation, and in each meeting will allocate time to discuss any new studies that might inform the safety or conduct of this study. According to best estimates, the rate of adverse/serious adverse events using rTMS safely is approximately 0.1% (Dobek et al., 2015, *Neuropsychiatr Dis Treat.*). Therefore, if a single seizure is reported in the current study, the DSMB will carefully evaluate whether some risk factors were missed

during the consent and TMS contraindications screening (namely: sleep deprivation, a personal or family history of seizures, or neurological disorders such as moderate-to-severe traumatic brain injury, multiple sclerosis, or stroke). If we observe a seizure where no such prior indicators are identified by the DSMB, the study will be suspended while we revise our rTMS protocol, and consider alternative stimulation parameters (e.g. lower rTMS dose), or targets (e.g. other nodes of the brain's value and effort computation circuits).

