### **3. Study Design**

*3.1. Describe the study design (e.g., observational; randomized placebo-controlled clinical trial, etc.)*

This is a brain stimulation / HC arm of an existing protocol (#19-053). The current protocol describes a clinical trial where we will focus on the causal effect on decision-making of rTMS targeting dACC using a fully randomized, within-subjects, sham- controlled experimental design.

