## NONINVASIVELY MODULATING MOTIVATIONAL BRAIN REGIONS

- The protocol will recruit male and female adults (18-55 years old) of any ethnic background. All recruited participants will be capable of providing informed consent.
- Participants will have 12 or more years of education and the ability to provide informed consent independently.
- Exclusion criteria will be: any condition that would prevent the subject from being able to complete the protocol, prior history of neurological disease or any history of seizures (including prior history of TBI; i.e., any loss of consciousness  $\geq 1$  minute), not fluent in English, any contraindications to MRI or TMS (**Appendices 3-4**), history of substance abuse (excluding moderate alcohol or marijuana usage), a medical diagnosis of psychosis or mania, or stable doses of antipsychotics or mood stabilizers taken for less than two months.
- Participants who are found to have falsely represented any factors which should exclude them from the study, or who are unable to follow the study protocols for study session attendance may be withdrawn prematurely from the study.
- To reduce the possible spread of COVID-19, during the SARS-CoV-2 pandemic any participants who answer “yes” to any of the items in Question 34 of the Phone Screen (**Appendix 1**) will be excluded from the study at this time.

*4.3. Indicate specifically whether you will include each of the following special populations: (You may not include members of the above populations as subjects in your research unless you indicate this in your inclusion criteria.)*

The study will not recruit from the following special populations: adults unable to consent, individuals who are not yet adults, pregnant women, or prisoners.

*4.4. Indicate if you excluding any particular populations (e.g., women, children, persons not fluent in English, a particular racial or ethnic group, etc.) and provide justification.*

Individuals not fluent in English will have difficulty performing the behavioral assays used in the current protocol, and will find it difficult to understand the study protocols to the point where they are capable of providing truly informed consent. Accordingly, proficiency in the English language is a requirement for the current protocol.

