## **6. Study Timelines**

### *6.1. Describe:*

Participants recruited for the study will be invited to complete three experimental sessions as soon as it is convenient for them to come in. The three experimental sessions will include one MRI scan (1-2 hours per scan). The first session will include all questionnaires and assessments (maximum time: 170 minutes, see Table 1). The second and third sessions will include rTMS administration including motor thresholding ( $\approx 20-40$  minutes), neuronavigation ( $\approx 10-20$  minutes) and rTMS delivery ( $\approx 3-20$  minutes, depending on the specific pulse sequence). The total rTMS session will last  $\approx 1-1.5$  hours, and will be immediately followed by an MRI scan (total session time: 3-4 hours for day 1, 4-5 hours for day 2). It is expected that data collection targets will be reached by September, 2022.

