## NONINVASIVELY MODULATING MOTIVATIONAL BRAIN REGIONS

contractions of the scalp muscles can cause discomfort or headache that usually go away promptly with nonprescription medication. The noise of the TMS magnet may affect hearing, so participants will be fitted with earplugs. Like MRI, TMS involves the use of a powerful magnet. Thus TMS will not be performed on people who have pacemakers, implanted pumps or stimulators, or who have metal objects inside their heads. The risk of inducing seizure with rTMS is considered very low at <0.1%. However, certain factors increase the risk of seizure such as sleep deprivation, family history of seizures, polypharmacy, alcohol use, and previous neurological conditions. Participants will be carefully screened for these factors to ensure that risk of seizure is minimized (**Appendix 4**).

- The CBRR and MRN are both located on the UNM North Campus, in close proximity to the UNM-ER. Therefore, participants will have rapid access to an emergency facility should an unforeseen medical emergency occur during testing.
- Participants will be told that they will only win a \$20 merchandise card on the primary task of interest (Bandit task) if they perform it well. However, at the end of the task all participants will receive the same compensation regardless of task performance. This protocol is used to ensure high motivation to perform the Bandit task, but may lead some participants to feel deceived at the end of the study. Accordingly, the reason for this procedure—i.e. “to ensure participants are motivated to try their best on the Bandit task”—will be explained clearly during a debrief at the end of the experimental session.
- During the SARS-CoV-2 pandemic, the current study’s procedures will be in accordance with the guidelines provided by the State of New Mexico and UNM-HSC Office of Research for maintaining physical distancing and face coverage. While supporting the efforts to reduce the spread and risk of infection, COVID-19 exposure is a potential risk associated with this study.

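### Section 14 requires no hold on stimulation while the DSMB reviews a seizure, and states no study-level action if a listed risk factor turns out to have been missed

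*Combined protocol and SAP*

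**What the plan says.** Section 14 is the only place in the protocol body with a seizure rule, and the rule has two steps.

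- **Trigger and review:** "if a single seizure is reported in the current study, the DSMB will carefully evaluate whether some risk factors were missed" at consent and at the TMS contraindication check. The factors to look for are "sleep deprivation, a personal or family history of seizures, or neurological disorders such as moderate-to-severe traumatic brain injury, multiple sclerosis, or stroke".
- **Suspension:** "If we observe a seizure where no such prior indicators are identified by the DSMB, the study will be suspended". The suspension is for revising the rTMS protocol and considering other doses or targets.

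The same section promises "prompt and frequent reporting of safety data (i.e., adverse/serious adverse events) to the DSMB" and to the Human Research Protections Office, alongside an annual DSMB review.

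Three other provisions are relevant.

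- Section 4.2 says that "Participants who are found to have falsely represented any factors which should exclude them from the study" may be withdrawn early.
- Section 12 requires visits to be at least 24 hours and at most two weeks apart.
- Section 18 relies on careful screening with the Appendix 4 form and says: "The risk of inducing seizure with rTMS is considered very low at <0.1" per cent.

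**The concern.** Under the stated rule, suspension is one possible result of the DSMB's evaluation. It is not what happens while the evaluation is under way. Two situations are left without an instruction.

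1. **Between the seizure report and the DSMB's conclusion.** The cause is unknown in this period, and no time limit is set for reaching a conclusion. A participant between visits can fall due for TMS within days. If the stimulation was the cause, that participant could receive the same parameters.
2. **When a listed factor was missed.** The text gives no hold, no correction of the screen, no re-screening of others and no condition for resuming. Yet a screening failure is the finding most likely to apply to other people already enrolled.

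What is at stake is the safety of healthy volunteers. No estimate or test in the trial depends on it.

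**Working it through.** The plan gives no figure for this rule, so there is none to reproduce. The check has a textual part and a part on size.

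**Text.** The rule has three states:

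| State after a reported seizure | Action stated in the protocol body |
|---|---|
| DSMB evaluation in progress | Prompt reporting; no hold and no deadline |
| No prior indicator identified | Study suspended and rTMS protocol revised |
| A prior indicator identified | None at study level |

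Sections 4, 7.2, 9.2, 12, 15, 18 and 33 do not fill the two empty states. Section 4.2 is permissive, applies to the individual concerned, and turns on false representation, so it does not reach a factor that the screen failed to pick up. Section 7.2 sets no safety endpoints. Section 15 covers withdrawal by the participant. Section 18 offers screening and closeness to an emergency department.

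**How often the rule would be used.** Inputs:

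- Participants: 42 (section 5.2).
- Seizure risk: below 0.1% (section 18), taken at its ceiling. The protocol does not say whether this is per person or per session.
- Active sessions: one per person. This is inferred from the "fully randomized, within-subjects, sham- controlled experimental design" in section 3.1 and from section 6.1: "The second and third sessions will include rTMS administration including motor thresholding". With one active session each, the per-person and per-active-session readings coincide.

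P(at least one seizure) = 1 - (1 - p)^n

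- p = 0.001, n = 42: 1 - 0.999^42 = 0.041.
- p = 0.001, n = 34 (42 × 0.8 = 33.6, using the 20% attrition in section 5.3): 1 - 0.999^34 = 0.033.
- Sensitivity, n = 42: 2.1% at p = 0.0005, and 19.0% at p = 0.005. The second rate is five times the protocol's ceiling and is shown only for range.

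**Exposure during a review.** The protocol gives neither the enrolment period nor the length of a review. Assume 12 to 24 months of steady accrual, a review of 1 to 4 weeks, and 30.44 days per month.

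- Active sessions per month: 42/24 = 1.75 to 42/12 = 3.5.
- Falling due during a review: 1.75 × 7/30.44 = 0.40 to 3.5 × 28/30.44 = 3.22.
- Averaged over the whole trial: 0.04115 × 0.4024 = 0.017 to 0.04115 × 3.219 = 0.13 active sessions.

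These are exposures, not harms. At 0.1% per session the expected number of further seizures is about 0.00002 to 0.00013. If the risk after a first event were as high as an assumed 5% per session, the upper figure would be 0.13 × 0.05, about 0.007.

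**The case against.** The strongest reply is that the existing protection is already substantial. One seizure is the lowest possible trigger. Reporting is prompt and goes to two bodies, and the DSMB members are chosen for experience with seizure monitoring. If the review points to the stimulation rather than to a missed factor, the study is suspended. The listed factors are largely covered by the exclusion criteria and the TMS screen, so a missed factor is the failure of a check that the protocol already requires. The expected exposure is also tiny.

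Most of this stands, and it is why the point is minor. It does not supply the missing instruction. Reporting governs who is told, not whether the next participant is stimulated. A screen that has just failed once is weak reassurance for others who passed it.

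Three stronger readings are tempting, and the documents do not support them.

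- A reader might infer that the protocol obliges stimulation to continue, or prevents a pause. It does neither. It leaves a pause to discretion.
- A reader might infer that a seizure could wait for the annual DSMB meeting. The single-seizure trigger and the prompt reporting say otherwise, although no deadline is given.
- A reader might count both TMS visits and put the chance of a seizure at 1 - 0.999^84 = 8.1%. Section 18 gives its rate for rTMS. Under section 12, sham delivers no real magnetic stimulation, and thresholding uses single pulses, for which no rate is given. The 84-visit figure therefore has no basis in the documents.

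**Conclusion.** The gap is real but minor. In the protocol body, suspension after a seizure follows only if the DSMB identifies no prior indicator. No hold is required during its evaluation, and no study-level action is stated if a listed indicator was missed. Appendices 4 and 28 were not available, so this cannot be taken as a statement about the full set of study procedures.

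The chance that the rule is needed is at most about 4.1%, assuming 0.1% per person and one active session in each of 42 participants. The exposure figures rest further on the assumed accrual and review times. The point still merits a change because the wording, followed literally, allows stimulation while the cause is unknown and leaves others who passed the same screen unchecked.

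**What to change.** Keep the single-seizure trigger, the DSMB instruction and the list of factors. After the trigger sentence, insert:

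*All TMS in all participants stops on the day the seizure is reported and does not restart until the DSMB gives written agreement. If a listed risk factor was missed, the screening is corrected and every participant with TMS sessions remaining is re-screened for it before stimulation resumes.*

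Keep the existing sentence on suspension and revision of the rTMS protocol. With a hold in force, the lack of a deadline for the DSMB no longer exposes anyone.

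Then add a bounded visit rule. Participants on hold may exceed the two-week limit in section 12, up to a stated maximum agreed with the DSMB. A participant held between sessions 2 and 3 is not counted as a completed active/sham pair under a single protocol if the gap exceeds that maximum or if the rTMS protocol is revised in the meantime. Without this bound, a hold could put an open-ended gap, or two different stimulation protocols, inside one within-subject comparison.

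The cost is a wording amendment and the DSMB's agreement. Eligibility criteria and the planned sample size do not change. If a seizure does occur, the downside is a pause, some longer visit gaps, and possibly a few incomplete pairs.
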